**Operations Office**

[name] • [name] • [contact] • [contact]

A phrase was added to the end of the third sentence of the (now) eighth paragraph of Section II to indicate that treatment of early prostate tumors which may be found during this study "... involves a significant risk of side-effects".

The final sentence of Section III was amended to delete the word "alternative".

6. The Hawaii Minority Based CCOP and the Greenville CCOP (South Carolina) have been added as participating Study Centers. This change is reflected in Section 19.6.

Replacement pages are enclosed for pages 2, 15, 16, 22 - 25 and 25a, 42 - 44, 59 - 62, 66 and 68. Please insert them into your copy of the protocol. Page 25a was added to prevent extensive repagination.

This memorandum serves to inform the Statistical Center, CALGB and ECOG.

cc: PCPT Statistical Center Staff - [name]  
[name]  
[name].  
[name].  
[name].  
Merck, Sharpe and Dohme - [name]., Ph.D.  
Axion Pharmaceuticals - [name]  
ECOG  
CALGB

July 1, 1995

To: PCPT Principal Investigators  
PCPT Data Managers

From: [name]  
Chairman  
Southwest Oncology Group

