**AMENDMENT #3**

The study referenced above has been amended as outlined below:

1. [name] "Diet Ancillary Study" has been added as Appendix 19.7. Associated changes in the protocol body include the addition of [name] address on page 2, the addition of Objective 1.8, the addition of background information on the dietary assessment on page 18, mention of the dietary assessment in Section 7.6, the addition of Section 7.6e, the addition of the "Food Frequency Questionnaire" and anthropometric measurements to the Study Calendar (Section 9.0) and the addition of a sentence in Section 11.14 covering Objective 1.8.
2. Sections 8.2 and 16.0 (page 36) have been amended to clarify the regulatory requirements for the reporting of sexual side-effects in participants on this study. The alternative grading scales for Impotence, Loss of Libido and Ejaculate Volume provided in Section 8.2 are to be used only for eligibility purposes and routine reporting. They are not to be used for the determination of the need for an ADR report. The grading scales provided in the Southwest Oncology Group Toxicity Criteria (see Section 19.1) are to be used for the determination of the need for an ADR report. Additionally, the Southwest Oncology Group ADR form for reporting ADRs is enclosed for the use of PCPT institutions.
3. [name], M.S. and [name] M.S. have been added as statisticians for this study, replacing [name], M.S. This change is reflected on page 2.
4. A typographical error in the calculation of the PSA Index in the next to the last paragraph on page 15 was corrected.
5. Two of the risk-factors for CHD in Appendix 19.3 were deleted (cholesterol level and male gender) to be consistent with the algorithm for risk counselling. Also, a formula for calculating Ideal Body Weight was added.

6. The Pathology Review Procedures in Appendix 19.4 were updated.
7. The Colorado Cancer Research Program CCOP, the Louisiana State University CCOP in New Orleans, and the Main Line Health CCOP have been added as participating Study Centers. This change is reflected in Appendix 19.6.

Replacement pages are enclosed for pages 2, 4, 15, 18, 23, 24, 26, 27, 33, 36, 46, 57 - 61, 65, 66, 68 and the Southwest Oncology Group ADR Form. Pages 70 - 80 have been added as the new Appendix 19.7. Please insert them into your copies of the protocol.

This memorandum serves to inform the Statistical Center, CALGB and ECOG.

cc: PCPT Statistical Center Staff - [name]  

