### **PSA Index**

At years 1 - 6 following randomization, all participants will have a PSA screening for prostate cancer. Consider a placebo arm participant at the first screening, Year 1 from randomization. PSA for this participant will be reported as "elevated" if it is  $\geq 4.0$  ng/ml. Since finasteride lowers the PSA, a PSA index is required to impose a comparable cutoff for the finasteride arm to ensure that an equivalent number of finasteride arm participants are biopsied due to PSA. Without an index, the same cutoff of 4.0 ng/ml would reduce the sensitivity of the PSA screening on the finasteride arm.

A critical assumption that is needed to make the PSA Index valid is that finasteride reduces the PSA of each participant by the same percentage. This percentage can be estimated from Merck's data on BPH patients treatment with finasteride. Their data indicates that the finasteride arm PSA median will have been reduced by 48% of baseline at Year 1 (95% confidence interval 45 - 52%). (51) Using the Merck data, the PSA Index (factor) for the finasteride arm will be  $(1 - .48) (4.0) = 2$ .

Since the Merck data involved men with possibly different biological characteristics the factor of 2 will be used only for the initial estimate of the PSA Index in the PCPT. During the course of the PCPT, the PSA Index will be revised based on study estimates of the percent reduction in PSA

on the finasteride arm. The timing of the first estimate will be set such that a sufficient sample size is available to obtain an accurate estimate, say to within  $\pm 5\%$ . Subsequent estimates, given a greater sample size, will be more accurate.

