Each participant has the potential of a PSA-induced prostate biopsy at each year of treatment. Once a participant has had a negative PSA-induced prostate biopsy, however, the criterion for a PSA-induced prostate biopsy changes. Consider a placebo arm participant at the second screening. Year 2 from randomization, who had a negative PSA-induced prostate biopsy at Year 1. PSA for this participant will be reported as "elevated" under the following conditions: 1) PSA 10 ng/ml, or 2) 50% increase over the previously reported "elevated" value. For the first condition, if we make the assumption again that PSA is reduced by 48% for each participant, the repeat biopsy PSA index for the finasteride arm will be  $(.48)(10) = 4.8$  ng/ml. For the second condition, since a percent change in PSA has the same meaning on both arms, a 50% increase in PSA will also be an indication for a repeat biopsy on the finasteride arm.

The expected PSA-induced biopsy rate can be estimated from existing data. A total of 21,797 men were screened for prostate cancer as part of the Prostate Cancer Awareness Week. (52) The combined biopsy rate due to DRE and PSA was 5.2% (95% confidence interval 4.9 - 5.5%). Therefore the percent of men screened with a PSA 4.0 ng/ml was 5.2%. In a Minnesota screening study, 28/305 men of age 50 - 79 had a PSA 4.0 ng/ml for a rate of 9.2% (95% confidence interval 6.2 - 13%). (53) Another study from Abbott reported 5/394 (1.3%) of healthy men of age > 40, and 118/520 (23%) of men with BPH, prostatitis, or other genitourinary diseases had a PSA 4.0 ng/ml for a combined rate of 14% (95% confidence interval 11 - 16%). (54)

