Prior to obtaining PSA specimens, the degree of study drug adherence must be ascertained by PCPT staff. **This is extremely important because non-adherence immediately prior to specimen collection will affect the accuracy of the PSA Index. Non-adherence to the study drug that is not reported to PCPT staff may result in an unnecessary recommendation for prostate biopsy. This information is to be communicated to the participant.** If it is determined that in the two weeks prior to the visit that the participant has not taken any study drug, delay collecting the PSA specimen for two months.

Monoclonal PSA determinations will be performed in the Central Laboratory Facility (CLF) and will be blinded to participants and investigators. For both participants receiving finasteride or placebo, PSA determinations will be reported as either "NOT ELEVATED" or "ELEVATED". A numerical PSA value will be reported on all participants with an "ELEVATED" PSA at annual examination. The reported PSA values for participants receiving placebo will be the measured value. The reported PSA values for participants receiving finasteride will be adjusted by a factor calculated by the Statistical Center (with monitoring by the Data and Safety Monitoring Committee).

The adjustment factor will be calculated by first determining the percentage of placebo-treated participants with elevated PSA. Then, for the finasteride-treated participants, the value of PSA for which the same percentage of participants will be elevated will be identified. This value will be used to calculate the factor for adjusting the PSA for participants treated with finasteride. This method will prevent PSA bias between placebo- and finasteride-treated participants for whom a biopsy is recommended. Details of this procedure and justification can be found in the Background Section of this protocol under "PSA Index".

If the participant has an "ELEVATED" PSA a prostate biopsy (see Section 7.7) is recommended. Decisions regarding appropriate follow-up care for the participant should be based on this PSA value and the clinical judgment of the investigator. If a repeat PSA value is deemed necessary, the test *must* be performed by the Central Laboratory Facility. This is essential as, without knowledge of the participant's actual treatment, a value from an outside laboratory is meaningless.

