Participants with an elevated PSA who have benign tissue upon pathologic examination by the Pathology Core Laboratory are recommended to have a TRUS and biopsy at subsequent years if one or both of two conditions are met: (1) PSA increase of 50% or more above the PSA value that prompted the recommendation of the original biopsy or (2) adjusted PSA greater than 10 ng/ml.

PSA values will be provided for participants who are off treatment. These values will not be indexed (adjusted).

- c. All participants will be evaluated according to the AUA Symptom Scale annually.
- d. All participants will complete a diet questionnaire and have physical measurements performed at the First Annual Visit only.
- e. Participants who are removed from treatment for any reason other than development of prostate cancer will be followed twice annually for the remainder of the seven years. One contact will be by phone for a general health status update, and the other contact will be a Study Site visit for annual DRE and PSA. The requirements for endpoint reporting, management of abnormal DRE and/or "ELEVATED" PSA as well as pathology submission will be the same as for participants who remain on treatment.

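### The initial finasteride-arm repeat-biopsy PSA threshold multiplies by the fraction of PSA removed: 4.8 ng/ml should be 5.2 ng/ml (5.0 with the rounded factor of 2)

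*Supplement*

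**What the plan says.** The PSA Index part of Section 2.0 assumes that finasteride lowers every man's PSA by the same percentage. It takes 48% from the manufacturer's BPH data ("95% confidence interval 45 - 52" per cent). The placebo cutoff of 4.0 ng/ml becomes (1 - .48)(4.0) = 2 ng/ml on finasteride, and the section adds that "the factor of 2 will be used only for the initial estimate of the PSA Index in the PCPT".

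The section then turns to men who have had a negative PSA-prompted biopsy. On placebo, a later PSA counts as elevated at 10 ng/ml or after a 50% rise. For the 10 ng/ml criterion it reasons "if we make the assumption again that PSA is reduced by 48% for each participant, the repeat biopsy PSA index for the finasteride arm", and it sets that index at 4.8 ng/ml, computed as .48 times 10.

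Section 7.6b gives the rule for conduct. The Statistical Center finds the percentage of placebo men with an elevated PSA, and then for finasteride "the value of PSA for which the same percentage of participants will be elevated will be identified". That paragraph closes with a pointer back: "Details of this procedure and justification can be found in the Background Section of this protocol under" the PSA Index heading. The absolute repeat-biopsy criterion in 7.6b is "adjusted PSA greater than 10 ng/ml"; no unadjusted finasteride cutoff is given there.

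**The concern.** The two conversions rest on the same assumption but use opposite fractions. If PSA falls by 48%, then 52% remains, so a finasteride cutoff equivalent to a placebo value is 0.52 times that value. The first conversion does this and the second does not.

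The index exists to give the two arms comparable cutoffs, so that PSA prompts biopsy about equally often in each. A repeat threshold set too low would send finasteride men with an earlier negative biopsy back at a lower placebo-equivalent PSA than placebo men. The section is also the one to which 7.6b sends the reader for the details of the procedure, so a reader or programmer following that pointer meets a raw threshold that does not match an adjusted PSA of 10 ng/ml.

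**Working it through.** **Inputs** (Section 2.0, PSA Index): assumed reduction r = 0.48, interval 0.45 to 0.52; placebo cutoffs 4.0 ng/ml (first biopsy) and 10 ng/ml (repeat biopsy).

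**The plan's own figures**
- First biopsy: (1 - 0.48) × 4.0 = 2.08, printed as 2.
- Repeat biopsy: 0.48 × 10 = 4.8, as printed. Expression and product agree, so this is not a lost "1 -" in the text extraction; a lost term would have left 5.2 as the result.

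**The consistent value**
- Rule: finasteride cutoff = (1 - r) × placebo cutoff.
- (1 - 0.48) × 10 = 5.2 ng/ml.
- With the rounded factor of 2: 10 / 2 = 5.0 ng/ml.

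**Why it is easy to miss.** At the 4.0 cutoff both fractions round to the same number: 0.52 × 4.0 = 2.08 and 0.48 × 4.0 = 1.92. They separate visibly only at 10.

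**Size of the gap**
- Against 5.2: 5.2 - 4.8 = 0.4 ng/ml; 1 - 4.8/5.2 = 7.7%.
- Against 5.0: 5.0 - 4.8 = 0.2 ng/ml; 1 - 4.8/5.0 = 4.0%.

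**Holding 4.8 fixed while the true reduction varies** (placebo equivalent = 4.8 / (1 - r))

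| Reduction r | Consistent cutoff 10(1 - r) | Shortfall of 4.8 | Placebo equivalent of 4.8 |
|---|---|---|---|
| 0.45 | 5.5 | 0.7 | 8.73 |
| 0.48 | 5.2 | 0.4 | 9.23 |
| 0.50 (factor of 2) | 5.0 | 0.2 | 9.60 |
| 0.52 | 4.8 | 0 | 10.0 |

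Across the stated interval 4.8 is too low, or exactly right at the 52% limit. It is never too high.

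**Who could be affected.** Only finasteride men with an earlier negative PSA-prompted biopsy and a later measured PSA between 4.8 and 5.2. They must also not have met the 50%-rise criterion, so the value that prompted the first biopsy must have exceeded at least 4.8/1.5 = 3.20 ng/ml measured (5.2/1.5 = 3.47 at the top of the window). On the placebo scale, 3.20/0.52 = 6.15. Men in the window with an abnormal DRE would be recommended for biopsy anyway, so the group is smaller still.

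**Amendment history.** Amendment #3 records: "A typographical error in the calculation of the PSA Index in the next to the last paragraph on page 15 was corrected". Amendment #5 later re-issued those pages ("Replacement pages are enclosed for pages 2, 15, 16, 22 - 25 and 25a"). The current text still carries (.48)(10) = 4.8.

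**The case against.** The best case against the point is that this is a stale worked example in the Background. Section 7.6b states the operative rule on adjusted PSA, and its factor is obtained by matching percentages elevated, under Data and Safety Monitoring Committee oversight, not from the 48% figure. The pointer back to the PSA Index section closes the paragraph on the adjustment factor and comes before the repeat-biopsy rule. Nothing in the documents shows that 4.8 was ever programmed.

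The gap is also close to tolerances the plan accepts. Rounding 2.08 to 2 is itself a 3.8% change, the first trial estimate of the reduction is wanted only to within about 5%, and 4.8 sits at the edge of the range implied by the interval. Biopsy during follow-up is only recommended, and men still on treatment have a seven-year biopsy. Extra finasteride-arm biopsies would, if anything, work against showing a benefit.

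All of this stands as a limit on reach. None of it makes 4.8 follow from a 48% reduction: the sentence restates that assumption and then gives a number that would need PSA to fall to 48% of its value. Nor is the figure offered as a loose illustration. The section says what the repeat-biopsy index will be, which makes it a stated decision threshold.

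**Conclusion.** The figure is wrong as written. Under the section's own assumption and rule, the finasteride repeat-biopsy threshold is 5.2 ng/ml, or 5.0 with the rounded factor, not 4.8. The size rests on the uniform 48% reduction. If the true reduction were 52%, 4.8 would happen to be right; elsewhere in the interval it is up to 0.7 ng/ml too low.

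Severity is minor. The 48% was only the initial estimate, the factor in Section 7.6b governs in practice, and the 50%-rise trigger is correctly the same in both arms. The endpoint, alpha, power and sample size do not depend on this number.

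**What to change.** In the PSA Index part of Section 2.0, replace the repeat-biopsy expression with (1 - .48)(10) = 5.2 ng/ml. Alternatively, delete the raw figure and state that the Section 7.6b adjustment factor applies to both the first and the repeat trigger. Confirm that the Statistical Center's program applied the adjusted-PSA rule of 7.6b and did not use 4.8 as a raw cutoff. The cost is one line of protocol text and one program check.

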### **Study Features**

A Touch-Tone telephone system at the Southwest Oncology Group Statistical Center will be used to randomize participants. The Southwest Oncology Group will create and supply each Study Center with a Study Manual. Training will be mandatory for designated personnel at all Study Centers. Training will take place prior to study activation. Additional training may be required as the study progresses.

The primary mechanism for submitting data forms to the Southwest Oncology Group Statistical Center will be via facsimile transmission. In some instances postal services may be utilized. The Southwest Oncology Group Statistical Center will communicate with participating Study Centers and/or Study Sites using facsimile transmission and postal service. Statistical Center communications will include information regarding follow-up schedules. Details regarding data submission, corrections and follow-up are found in the Study Manual.

### **Quality of Life**

It is generally recognized (and it is Southwest Oncology Group policy) that assessment of quality of life (QOL) must involve measurement of multicomponents of a person's functioning. (29 - 35) There is consensus that QOL encompasses physical, role, emotional and social functioning, and symptom status and that it is important to assess these dimensions not only in cancer clinical trials but in any type of randomized clinical trial. Study participant report of QOL is required because it conveys additional information not present in the clinical report of how the individual is functioning. The reality of this additional perspective has been documented in research addressing the extent of agreement in physician and patient report of patient functioning. (36 - 40)

Multidimensional assessment of QOL is just as important and informative in chemoprevention trials. For example, QOL is assessed in the Postmenopausal Estrogen/Progestin Interventions Trial (PEPI) currently being conducted by the National Heart, Lung and Blood Institute (NHLBI). Goals of this research include assessing the protective effect of postmenopausal hormonal interventions for coronary heart disease; the role of such intervention in preventing osteoporosis

is a secondary research question. QOL is also being assessed in the Breast Cancer Prevention Trial (BCPT) of tamoxifen (National Surgical Adjuvant Breast and Bowel Project P-1 Protocol). In both instances, QOL is assessed with a battery of measures. The BCPT is using the Medical Outcomes Study Short Form-36 (MOS SF-36), the primary QOL measure proposed for this study.

The MOS SF-36 is based on health status scales developed by the Rand Corporation for the Health Insurance Experiment in the 1970's. These scales were designed to assess multiple dimensions of health status and functioning in a healthy population. (41) Subsequently, these health status scales were revised and shortened for use in clinical trials with both healthy and sick populations; the psychometric properties of these scales have been amply documented. (35, 42 - 44) The MOS SF-20 and SF-36 are currently in use in many trials involving medical interventions; MOS SF-20 and 36 scales are currently being used in several Southwest Oncology Group trials. The MOS SF-36 has separate scales and items (which are not summed for a total score) to measure overall perception of health, change in health status, pain, physical, role, social, and emotional functioning, and energy/fatigue. We believe that the MOS is ideally suited for assessing the effects of finasteride on the health status and QOL of healthy men participating in this chemoprevention study.

Protocol- or treatment-specific items will also be included in other QOL assessments to measure the effect of finasteride versus placebo on the sexual functioning of study participants since the most frequently reported side effect of this treatment has been some degree of sexual dysfunction. The American Urological Association (AUA) Symptom Index will be administered as well. (45 - 47) The sexual functioning questionnaire, the AUA Symptom Index, and the MOS - SF will be administered according to the Study Calendar (Section 9.0).

Brief baseline demographic and lifestyle questionnaires will be administered once to all participants (see Study Calendar, Section 9.0).

#### **Cardiovascular Assessments**

In men over the age of 55, cardiovascular diseases are anticipated to occur 3 to 5 times more frequently than prostate cancer. In addition, approximately 1 of every 2 deaths recorded in men of this age are expected to be associated with cardiovascular disease. To monitor and interpret cardiovascular adverse drug reactions and deaths adequately, cholesterol measurements are obtained at the First Visit to characterize each participant's risk status. Using guidelines from the National High Blood Pressure Education Program, men will be classified as high risk, borderline high risk, or normal risk. (50) In line with the National Cholesterol Screening Guidelines, men who are found to have abnormal screening cholesterols will be appropriately referred for further evaluation and/or treatment. As a benefit to their participation, this adherence to National Screening Guidelines will assist healthy recruits in reducing their risk of heart disease.

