## **11.0 STATISTICAL CONSIDERATIONS**

- 11.1 OVERVIEW: The primary objective of this prevention trial is to assess whether participants randomized to receive finasteride for seven years will have a different proportion of prostate cancer than participants randomized to receive a placebo for seven years. Other objectives of this study are listed in the Objectives section of this protocol (Section 1.0) and include estimation of the side-effect rates associated with finasteride, assessment of the acceptability of long-term finasteride use by healthy participants, and assessment of the effect of finasteride on the sensitivity and specificity of DRE and PSA.

A study of 18,000 randomized subjects (9,000 placebo, 9,000 finasteride) is planned. The trial will be double-blind. The participants to be enrolled will be 55 years old, generally healthy, have a normal PSA, and be free of significant chronic comorbid disease, especially severe symptoms of BPH.

The participants randomized will be scheduled for prostate biopsy following seven years of study treatment. The primary outcome is the presence or absence of prostate cancer as assessed by the end-of-study biopsy or prior to seven years on study.

It is projected that accrual will be completed in three years, with approximately 3,600 subjects (20%) randomized in the first year and approximately 7,200 subjects (40%) in each of years two and three. It follows that the last biopsy will be completed ten years following the beginning of enrollment.

The validity of this study depends on a number of CRITICAL ASSUMPTIONS related to the ability to know when a participant is not adherent, between arm comparability for the

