placebo	side-effect percents		power
	placebo	finasteride	
1	1	2	.50
	1	3	.97
	1	4	.99
2	2	4	.86
	2	5	.99
	2	6	.99
5	5	8	.90
	5	10	.99
10	10	13	.67
	10	15	.99

11.12 CARDIOVASCULAR DISEASE: Because cardiovascular disease is common among the men of age 55 (eligibility ages of the participants to be enrolled) the power will be high to detect even small differences between the arms with respect to cardiovascular disease

incidence and events. For example, if the incidence rate for coronary artery disease (CAD) for participants on this study is estimated to be 25 per 1000 per year then there could be as many as 1575 diagnoses of CAD in the placebo arm, that is, 17.5% of the placebo arm participants. The 0.05 one-sided power to detect a 10% higher incidence of CAD in the finasteride arm (1733 incident cases or 19.3%) would be 91.4%.

- 11.13 **DATA AND SAFETY MONITORING:** An external Data and Safety Monitoring Committee (DSMC) will review the safety, mortality, side-effects, adherence, and potential violation of the assumptions necessary for trial validity. The DSMC will review unblinded trial monitoring data every six months.

The Data and Safety Monitoring Committee (DSMC) will be an independent panel of urologists, statisticians, epidemiologists, and ethicists (approximately 10 total members). PCPT Study Investigators will be excluded from membership in this committee, but may participate in the review of blinded data as necessary.

The DSMC will be provided with detailed reports of all adverse events and deaths, including summaries of hospitalization discharges and deaths.

Side-effect data will be monitored more closely for the first cohort of 3600 subjects than for those who follow. The purpose of this monitoring will be to confirm previous finasteride studies which claimed minimal side-effects. Adherence data will be reviewed in order to provide the opportunity to implement additional adherence measures.

A monitoring system for detecting deviations from the CRITICAL ASSUMPTIONS will be active throughout the trial. This system will be used to generate data for DSMC review. Because of the fragility of this trial with respect to conformity to CRITICAL ASSUMPTIONS, and the resulting complexity of the monitoring tasks, no specific stopping rules are specified.

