- 11.14 **SECONDARY ANALYSES AND SECONDARY OBJECTIVES:** Beyond the analysis of the primary outcome described above, the probability of prostate cancer at seven years will be modeled using standard methods for categorical data, with explanatory variables including age, race, family history, gland size, laboratory data, etc. The probability of side-effects will be modeled using information on adherence (and other covariates).

Objective 1.2 (finasteride's effect on stage and grade) will be analyzed by comparing between the arms the grade and stage distribution of the incident cases. Data will come from pathology review of biopsy specimens. Standard categorical data analysis methods will be used.

Objectives 1.3, 1.4, 1.5, and 1.7 (toxicity, side-effects, mortality, BPH, and quality of life) will be analyzed by comparing between the arms the rates of events and magnitudes of effects. The data will come from reports of events, participant interviews, and side-effect and quality of life questionnaires. Standard categorical data methods, including methods for ordered categorical data will be used.

Objective 1.6 (finasteride's effect on screening modality) will require detailed pathology data as well as an analysis of the data generated from the procedures used to adjust PSA levels. Should finasteride prove to be efficacious in preventing prostate cancer then it will be important to be able to recommend to practitioners methods for monitoring for prostate cancer in those taking finasteride. Additional data addressing this issue may become available from trials of the use of finasteride in BPH.

Objective 1.8 (association of dietary fat and an increased risk of prostate cancer) will be approached as detailed in Appendix 19.7, which outlines methods of data collection and analysis.

Objective 1.9 (cohort study of CAG repeat length) will be approached as detailed in Appendix 19.8.

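### Coronary risk status is measured on randomized men in order to interpret cardiovascular events and deaths, but no cardiovascular or mortality comparison prespecifies adjustment for it.

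*Supplement*

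**What the plan says.** **Purpose and availability.** Section 2.0, Cardiovascular Assessments, states: "To monitor and interpret cardiovascular adverse drug reactions and deaths adequately, cholesterol measurements are obtained at the First Visit". Each man is then placed in one of three risk classes (high, borderline high, normal). Section 7.1 has the coronary risk factors determined at the First Visit. It has total and HDL cholesterol assayed on First Visit serum for the men who go on to be randomized. Appendix 19.3 lists the factors: family history, smoking, hypertension, low HDL, severe obesity, diabetes, and prior cerebrovascular or peripheral vascular disease. Prior infarction or ischemia enters through the referral criteria of Section 7.1. The First Visit comes three months before randomization, so all of these are baseline variables.

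**Planned use.** Section 11.12 gives a power example: "The 0.05 one-sided power to detect a 10% higher incidence of CAD in the finasteride arm" is put at 91.4%. It describes no analysis model. Section 11.14 says that Objectives 1.3, 1.4, 1.5 and 1.7 (toxicity, side-effects, mortality, BPH, quality of life) "will be analyzed by comparing between the arms the rates of events and magnitudes of effects", using standard categorical methods. It also says that side-effect probability will be modeled with adherence and other covariates, which it does not name. Appendix 19.10, Section 5.0, compares mortality by Kaplan-Meier curves and a logrank test. Coronary risk status is named in none of these. By contrast, the primary analysis in Section 11.9 is a logistic model with prespecified covariates.

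**The concern.** The protocol measures coronary risk so that cardiovascular events and deaths can be interpreted, then does not say how the measurement will be used in comparing them. Section 2.0 expects cardiovascular disease to be three to five times as frequent as prostate cancer in this age group and to be associated with about half of all deaths. It is therefore a main long-term safety question in healthy men.

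Two things are at stake. The first is precision: a between-arm comparison that conditions on prognostic baseline variables has a better chance of detecting a modest excess than one that does not. The second is prespecification. The Data and Safety Monitoring Committee sees unblinded data every six months and works without specific stopping rules (Section 11.13). A covariate set chosen after data have been seen would be easier to challenge than one fixed in the protocol.

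**Working it through.** **Inputs from Section 11.0.**
- Size: "A study of 18,000 randomized subjects (9,000 placebo, 9,000 finasteride) is planned".
- Rate: "the incidence rate for coronary artery disease (CAD) for participants on this study is estimated to be 25 per 1000 per year". Over seven years, 9,000 × 0.025 × 7 = 1,575, which matches "1575 diagnoses of CAD in the placebo arm, that is, 17.5% of the placebo arm participants".
- Alternative: 1,575 × 1.10 = 1,732.5, printed as 1,733. 1,733/9,000 = 19.26%, printed as 19.3%.
- Test: one-sided 0.05, with no loss to follow-up applied.

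**Step 1: reproduce the stated 91.4%.** Use the unadjusted two-proportion normal approximation, with p0 = 0.17500, p1 = 0.19256, difference 0.01756 and pooled proportion 0.18378.
- Null standard error: √(2 × 0.18378 × 0.81622 / 9,000) = 0.005774.
- Alternative standard error: √[(0.175 × 0.825 + 0.19256 × 0.80744) / 9,000] = 0.005772.
- z = (0.01756 − 1.645 × 0.005774) / 0.005772 = 1.396, so power = 91.9%.
- With a continuity correction, power is 91.6%. A two-sided test would give 86.0%.

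The printed figure is thus a one-sided, unadjusted two-proportion calculation, reproduced to within about half a point.

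**Step 2: what adjustment adds.** If baseline covariates explain a share R² of the outcome variance, the effective size per arm is about 9,000 / (1 − R²). This approximation fits a standardized risk difference most directly. In a logistic model the gain appears as a larger conditional effect rather than a smaller standard error. **R² is not in the documents; the range below is an assumption.**

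| Assumed R² | Equivalent extra men | Per arm | Power |
|---|---|---|---|
| 0 | 0 | 0 | 91.9% |
| 0.01 | 1.0% | 91 | 92.1% |
| 0.02 | 2.0% | 184 | 92.3% |
| 0.05 | 5.3% | 474 | 93.0% |
| 0.08 | 8.7% | 783 | 93.6% |
| 0.10 | 11.1% | 1,000 | 94.1% |
| 0.13 | 14.9% | 1,345 | 94.7% |

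To give R² a scale, assume a normally distributed logit risk and 18.4% overall incidence. A c-index of 0.58 then gives a gain of about 1.4%, 0.66 gives 5.4%, 0.705 gives 9.5%, and 0.745 gives 14.7%. At 10% incidence the gains are smaller: about 3.4% at a c-index of 0.66 and 10.1% at 0.75.

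**Step 3: the three-level class alone.** Class shares and relative risks are also assumptions. With shares 25/35/40% (high, borderline, normal) and relative risks 2, 1.4 and 1, R² = 0.018 and the gain is 1.8%. With shares 20/30/50% and relative risks 4, 2 and 1, R² = 0.081 and the gain is 8.8%.

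**Step 4: sensitivity to fewer men at risk.** Section 11.12 credits every man with seven years, while Section 11.4 plans for 20% mortality and 15% loss to follow-up. As an illustration only (these sizes are not in the protocol), 7,000 per arm gives 85.0% unadjusted and 85.3% to 89.1% with a 1% to 15% gain. At 6,000 per arm the figures are 79.9% and 80.3% to 84.6%. The gain is then at most about 4 to 5 points.

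**The case against.** **The text does not commit to unadjusted analyses.** A reader might infer that Sections 11.12 and 11.14 require unadjusted comparisons, or that the risk data enter no analysis at all. The documents do not support that. Section 11.12 is an example of power. Section 11.9 likewise sizes its covariate-adjusted primary model with standard formulas for proportions, so the formula implies no particular test. Section 11.14 is silent on adjustment, uses nearly the same phrase about categorical methods for a model that does have explanatory variables, and leaves room for unnamed covariates in side-effect models. This objection stands: the accurate statement is that no adjustment is prespecified. It does not remove the point. The only covariate named for side-effects is adherence, which is measured after randomization, and Section 11.14 lists mortality separately from side-effects.

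**A covariate list for a secondary safety comparison could sit in a separate analysis plan.** None is shown, so silence alone would be no fault. The point therefore rests on a better use of data already collected for this stated purpose.

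**The gain may be small.** A reader might take 5% to 15% more men as the expected return. That needs R² of about 0.05 to 0.13, which the documents do not give. They offer reasons for caution: eligibility requires performance status 0 and excludes uncontrolled cardiac illness (Sections 5.2 and 5.13), which narrows the range of risk. Men with abnormal cholesterol are referred for evaluation or treatment, which may weaken prediction from baseline. This stands, and the lower end of the range must be shown.

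**Unadjusted comparison of randomized arms is valid.** That also stands. In addition, Objective 1.4 is to estimate mortality differences, and no power for mortality is claimed.

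**Conclusion.** The point holds as a modest, low-cost improvement in precision and prespecification. Coronary risk status is collected before randomization for the stated purpose of interpreting cardiovascular events and deaths, and no comparison of those outcomes names it as a covariate.

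The size depends on prognostic strength, which has to be assumed. From weak to strong, the gain equals about 1% to 15% more men, or about 2% to 9% with the three-level class alone. On the Section 11.12 contrast at 9,000 per arm, power moves from 91.9% to between 92.1% and 94.7%: a fraction of a point at the weak end, about 1 to 3 points for gains of 5% to 15%. Nothing here suggests bias, or that the stated 91.4% is miscalculated.

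**What to change.** In Section 11.14, for Objective 1.3 (cardiovascular events) and Objective 1.4 (mortality), prespecify a model with arm plus First Visit covariates: age, prior infarction or ischemia, smoking, hypertension, diabetes, and total and HDL cholesterol. Report the standardized risk difference from that model beside the unadjusted rates. Add one sentence to Section 11.12 saying that its power figure is for the unadjusted contrast. For consistency, name the same covariates for the mortality comparison in Appendix 19.10, Section 5.0.

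The cost is wording: no new visits, assays or participants. Before finalizing the list, confirm that prior infarction or ischemia is recorded for every randomized man, since Section 7.1 mentions it only within a referral criterion. The one analytic drawback is that conditional and marginal odds ratios differ; reporting a standardized risk difference deals with this.
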